Endpoints	
Primary Endpoint
 
 
Assessment of DLT during the first 4 weeks of treatment (cycle 1)
 
Determination of MTD
 
 
Secondary Endpoints
 
 
Progression Free-Survival (PFS)
 
Overall response rate (ORR)
 
Clinical benefit rate (CBR; complete response + partial response + stable disease without disease progression at 6 months)
 
Pharmacokinetic assessments of erdafitinib
 
 
Correlative Endpoints

	

• FGFR1 fluorescence in situ hybridization (FISH)

• Next Generation Sequencing (NGS) of baseline or archival tumor specimen

• Plasma tumor cell free [cf] DNA at baseline, at 4 weeks and at disease progression

• Serial measurements of serum phosphate, calcium, vitamin D, parathyroid hormone (PTH), FGF23, sFGFR2, sFGFR3 and sFGFR4

Trial Design	This is an open-label, multi-institution, phase Ib trial that evaluates the safety, tolerability, and anti-tumor activity of fulvestrant, palbociclib with erdafitinib in patients with ER+/HER2-/FGFR-amplified metastatic breast cancer (MBC).
Number of Patients	

• Minimum: 26 patients

• Maximum: 35 patients

Participating Institutions	

• Vanderbilt-Ingram Cancer Center (Coordinating Center)

• TBCRC (4 centers)

Duration of Therapy	In the absence of treatment delays due to adverse events, treatment will continue until: 

• Disease progression

• Inter-current illness that prevents further administration of treatment

• Unacceptable adverse event(s)

• Patients decides to withdraw from the study

• Significant patient non-compliance with protocol

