**Table 17.2.1**

		Number of Patients																	
		1	2	3	4	5	6	7	8	9	10	11	12	13	14	15	16	17	18
Number of Patients with DLTs	0	E	E	E	E	E	E	E	E	E	E	E	E	E	E	E	E	E	
	1	D	D	S	S	S	S	S	E	E	E	E	E	E	E	E	E	E	
	2	D	DU	D	S	S	S	S	S	S	S	S	S	S	S	S	E	E	
	3	DU	DU	DU	DU	D	S	S	S	S	S	S	S	S	S	S	S	S	
	4	DU	DU	DU	DU	DU	DU	D	S	S	S	S	S	S	S	S	S	S	
	5	DU	DU	DU	DU	DU	DU	DU	DU	DU	S	S	S	S	S	S	S	S	
	6	DU	DU	DU	DU	DU	DU	DU	DU	DU	DU	DU	DU	DU	DU	S	S	S	
	7	DU	DU	DU	DU	DU	DU	DU	DU	DU	DU	DU	DU	DU	DU	DU	DU	DU	
	8	DU	DU	DU	DU	DU	DU	DU	DU	DU	DU	DU	DU	DU	DU	DU	DU	DU	
	9	DU	DU	DU	DU	DU	DU	DU	DU	DU	DU	DU	DU	DU	DU	DU	DU	DU	
	10	DU	DU	DU	DU	DU	DU	DU	DU	DU	DU	DU	DU	DU	DU	DU	DU	DU	
	11	DU	DU	DU	DU	DU	DU	DU	DU	DU	DU	DU	DU	DU	DU	DU	DU	DU	
	12	DU	DU	DU	DU	DU	DU	DU	DU	DU	DU	DU	DU	DU	DU	DU	DU	DU	
	13	DU	DU	DU	DU	DU	DU	DU	DU	DU	DU	DU	DU	DU	DU	DU	DU	DU	
	14	DU	DU	DU	DU	DU	DU	DU	DU	DU	DU	DU	DU	DU	DU	DU	DU	DU	
	15	DU	DU	DU	DU	DU	DU	DU	DU	DU	DU	DU	DU	DU	DU	DU	DU	DU	

16												DU	DU	DU
17												DU	DU	
18														DU

**E:** Escalate to the next higher dose; **S:** Stay at the same dose; **D:** De-escalate to the previous lower dose; **DU:** De-escalate to the previous lower dose and the current dose will never be used again in the trial;

No new cohort of patients will be treated until the previous cohort has been fully evaluated for toxicity. All patients treated to determine the MTD will be part of the escalation portion of the trial.

Once the MTD is reached, the safety data will be analyzed and the expansion component of the study will be completed to assess tolerability and efficacy. Patients in the expansion component of the study will initiate study treatment at the respective MTD. Note that dose reduction within individual patients is allowed in the expansion component of the study. Dose reduction will be required for a given patient in case of grade 3 or 4 toxicities, or if grade 2 creatinine, bilirubin, AST, ALT, hyperphosphatemia or grade 2 GI toxicity lasting more than 2 weeks.

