#### Justification for RP2D based on $\geq 15$ out of 20 Tolerant Patients

	0.3	True probability of tolerability at MTD						
		0.5	0.7	0.75	0.8	0.9	0.99	
Probability of observing $\geq 15/20$ tolerable patients	0.00004	0.02	0.42	0.62	0.80	0.99	1.00	

#### Two-sided 95% Wilson Confidence Intervals\* for the Probability of Treatment Tolerance based on $\geq 15$ Tolerant Patients out of 20

Observed # of tolerant patients	95% Wilson confidence interval	
	Lower bound	Upper bound
15	0.53	0.89
16	0.58	0.92
17	0.64	0.95
18	0.70	0.97
19	0.76	0.99
20	0.84	1.00

\* We chose to calculate and report the Wilson score confidence intervals because of their good coverage properties, especially when the true proportions are at extreme values such as

being equal to or close to 1

([http://en.wikipedia.org/wiki/Binomial\\_proportion\\_confidence\\_interval](http://en.wikipedia.org/wiki/Binomial_proportion_confidence_interval)).

The recommended dose for phase II trials will be defined as the highest dose (at or below the MTD) at which  $\geq 15$  patients treated at the MTD (including patients from the escalation portion treated at that same dose level) can tolerate treatment for a minimum of 8 weeks in a row without development of the previously cited toxicities. The dose that will be used in the phase II study will be the most tolerable (i.e. with the least amount of  $\geq$  Grade 2 toxicities), as tested in this study. Study drugs will be given at the specified doses above until disease progression or unacceptable toxicity. As long as the above parameters are fulfilled (i.e. at least 15 out 20 patients are able to safely tolerate the combination at a given dose level stipulated by the study for 8 weeks in a row) the dose of study drugs in the expansion portion of the study (i.e. the highest tolerable dose; not necessarily the MTD) will move forward in phase II studies.

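### Section 17.2.1 gives two unranked rules for the RP2D that can select different doses, and an expansion at the MTD alone cannot establish a tolerable dose below it

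*Combined protocol and SAP*

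**What the plan says.** Three consecutive statements in the RP2D justification within section 17.2.1 bear on the choice of dose.

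- **Threshold rule.** "The recommended dose for phase II trials will be defined as the highest dose (at or below the MTD) at which" at least 15 patients treated at the MTD tolerate 8 consecutive weeks. Escalation patients treated at that same level are included in the count.
- **Least-toxicity rule.** "The dose that will be used in the phase II study will be the most tolerable", which the text explains as the dose "with the least amount of" toxicity of Grade 2 or above among the doses tested.
- **Closing sentence.** Provided at least 15 out of 20 patients tolerate the combination for 8 weeks, the expansion dose goes forward. That dose is described as "the highest tolerable dose; not necessarily the MTD".

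Section 17.1 likewise presents a highest tolerable dose as something additional to the MTD.

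On who is treated where, section 17.2.1 states: "Patients in the expansion component of the study will initiate study treatment at the respective MTD". Section 7.5 says the same. Section 17.2.1 plans at least 20 expansion patients, adds to the tolerability analysis only those escalation patients who were treated at the MTD, and uses escalation cohorts of 3. The synopsis gives a minimum of 26 patients and "Maximum: 35 patients".

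**The concern.** The threshold rule looks for the highest dose that passes; the least-toxicity rule looks for the dose with the least toxicity. They also use different yardsticks. Tolerance is judged against toxicities cited earlier in the section (Grade 3 or 4, or certain Grade 2 events that persist), whereas the second rule counts any event of Grade 2 or above. No text says which prevails, and the amount of toxicity is not defined as a count or a rate. A raw count would favour a 3-patient cohort over more than 20 patients at the MTD simply because of its size.

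Separately, the plan offers a dose below the MTD as a possible result, but puts no expansion patients at such a dose.

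Section 17.1 lists RP2D determination among the aims, and section 3.5 makes a later randomised phase II trial depend on it. Two analysts following the text could recommend different doses from the same data, one of them on very few patients.

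**Working it through.** **1. Reproduce the plan's table.** With X the number of tolerant patients, X ~ Binomial(n, p), and the table gives P(X ≥ 15) for n = 20. Recomputed at p = 0.3, 0.5, 0.7, 0.75, 0.8, 0.9 and 0.99: 0.00004, 0.02, 0.42, 0.62, 0.80, 0.99 and 1.00. All agree. The Wilson limits also agree, for example 0.53 to 0.89 for 15/20 and 0.84 to 1.00 for 20/20. The table is correct, but it is headed for the MTD only.

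**2. Can a level below the MTD reach 15 tolerant patients?** Inputs: total N of 26 to 35 (synopsis), at least 20 in expansion, all starting at the MTD, and cohorts of 3 (section 17.2.1). The MTD must itself have been tested in escalation, so at least one cohort of 3 was treated there.

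Most patients below the MTD = N − 20 − 3

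- N = 35: 35 − 20 − 3 = 12, over all lower levels combined
- N = 26: 26 − 20 − 3 = 3

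Both are under 15, even if every one of those patients tolerates treatment. A larger expansion, or more escalation patients at the MTD, lowers the bound further.

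**3. What would a lower-level recommendation rest on?** Possibly one cohort of 3. With z² = 3.84, the Wilson lower limit for 3/3 tolerant is n/(n + z²) = 3/6.84 = 0.44, so the interval is 0.44 to 1.00. For 0/3 with Grade 2 or higher toxicity, the upper limit is z²/(n + z²) = 3.84/6.84 = 0.56, so the interval is 0.00 to 0.56.

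**4. How often would the criterion be missed at the MTD?** The answer depends on the denominator. The closing sentence says 15 out of 20. The threshold rule says at least 15 after pooling with escalation patients at the MTD, so n is at least 20 + 3 = 23, or 26 with two such cohorts. P(miss) = 1 − P(X ≥ 15):

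| True tolerability | n = 20 | n = 23 | n = 26 |
|---|---|---|---|
| 0.70 | 1 − 0.416 = 0.58 | 1 − 0.771 = 0.23 | 1 − 0.940 = 0.06 |
| 0.75 | 1 − 0.617 = 0.38 | 1 − 0.904 = 0.10 | 1 − 0.985 = 0.015 |
| 0.80 | 1 − 0.804 = 0.20 | 1 − 0.973 = 0.03 | 1 − 0.998 = 0.002 |

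Holding the count at 15 while n grows also makes a poorly tolerated dose easier to pass. At true tolerability 0.50, P(X ≥ 15) is 0.021 for n = 20, 0.105 for n = 23 and 0.279 for n = 26. The published table describes only the first of these.

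**The case against.** The strongest defence is that there is really one gate. The closing sentence is the operational one: it ties progression of the expansion dose to the 15-of-20 criterion and does not mention the Grade 2 comparison. On that reading the least-toxicity sentence is loose prose, and the conditional wording implies that a dose missing the criterion does not go forward. This is a reasonable reading, and the implied negative branch stands. But the least-toxicity sentence is written as a selection rule, nothing subordinates it, and the implied branch does not say what the trial would then conclude.

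Two routes to a lower dose might be offered. Individual dose reductions are allowed, but those that are required follow from toxicities of the kind that count against tolerance, and no text credits such patients to the lower level. Section 10.6 allows new cohorts at other doses or schedules, but gives them no size and no tolerability rule; 20 at a lower dose on top of 23 at the MTD would make 43, above the maximum of 35.

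It is also fair to say that the listed primary endpoints are DLT and MTD, and that neither they nor the response and PFS analyses depend on the RP2D rule.

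A reader might infer that missing the criterion is likely. The documents do not support that. They state no expected tolerability; at 0.90 the chance of a miss is 0.01 even with n = 20, while at 0.50 it is 0.98; and pooling cuts the mid-range figures sharply.

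**Conclusion.** The concern holds as a contradiction in a decision rule for a stated aim. The two rules can select different doses from the same data, and the design as written cannot establish a highest tolerable dose below the MTD: at most 12 patients can be treated there (3 if N = 26), against a required 15.

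A reader might go further and infer that the rules always disagree. They do not: they coincide if the MTD is the lowest level tested, and the expectation that the least-toxicity rule favours the lowest level assumes that toxicity rises with dose. Nor does subtracting 20 from 35 prove infeasibility by itself, since 15 tolerant out of 15 would meet the count; the cohort of 3 at the MTD is what closes that gap.

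The bound assumes that the planned expansion is completed within the stated maximum; the split between escalation and expansion is derived here, not given in the plan. An amendment that stopped the MTD expansion early could change it. The miss probabilities depend on a denominator that the plan has not settled. No view is taken on which dose rule is right.

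**What to change.** The sponsor should reconcile the passages in section 17.2.1, and section 17.1 to match, so that they:

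- give one RP2D rule with one denominator, either 15 of 20 or a stated criterion for the pooled MTD patients, with the probability table and Wilson intervals recomputed if the denominator changes;
- state how the Grade 2 or higher comparison relates to the 15-patient criterion, and whether it is a count or a rate;
- state what the trial will conclude if the criterion is missed;
- either bring the description of the carried-forward dose as possibly not the MTD into line with the MTD-only expansion, or remove it;
- report any lower level with its own n and Wilson interval.

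This is a change of wording and needs no extra patients. The price is a narrower stated conclusion about doses below the MTD.

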#### 17.2.2. Secondary endpoints

Secondary endpoints defined in terms of percentages such as Overall Response Rate (ORR), Clinical Benefit Rate (CBR), and Progression-Free Survival (PFS) will be summarized and 95% CI for each percentage will be reported. The distribution of PFS will be estimated using the Kaplan-Meier method with censoring used as needed (e.g. if a patient is lost to follow-up, or analysis is done before all patients have had the event of interest). Median time to event and corresponding 95% CI will be reported along with Kaplan-Meier curves. The duration of PFS for patients who progress and then subsequently die will be the number of days between initiation of the study treatment and the date of when disease progression is first observed. Demographic and clinical characteristics will be summarized for all patients as percentages for categorical variables and as mean, standard deviation, median, minimum and maximum for continuous measures. Data will be collected using a centralized electronic case report form called **ON-line Clinical Oncology Research Environment = Oncore** (<http://www.vicc.org/ct/research/oncore.php>). An exploratory objective of this study is to determine the pharmacokinetics of the combination of erdafitinib, palbociclib and fulvestrant. The plasma samples from all patients will be assayed for erdafitinib and palbociclib concentrations using methods described in the Laboratory manual. Values below the assay LLOQ will be reported as 0.00 ng/mL. Missing values will be labeled accordingly. All concentrations below the LLOQ or missing data will be labeled as such in the concentration data listings. Concentrations below the LLOQ will be treated as zero in summary statistics. Calculation of PK parameters will include up to the last measurable concentration  $t_{last}$ . Pharmacokinetic parameters will be determined for all patients using non-compartmental method(s) using WinNonlin® Pro (Version 5.2 - Pharsight, Mountain View, CA). PK parameters listed in the table below will be estimated and reported.

$AUC_{0-last}$	The area under the plasma concentration-time curve from time zero to the last measurable concentration ( $T_{last}$ ) (mass x time x volume $^{-1}$ )
$AUC_{0-Inf}$	The area under the plasma concentration-time curve from time zero to infinity (mass x time x volume $^{-1}$ )
$AUC_{0-24}$	The area under the plasma concentration-time curve from time zero to 24 hours (mass x time x volume $^{-1}$ )
$AUC_{ex}^1$	Area under the plasma concentration-time curve extrapolated from the time $t$ to infinity as a percentage of total AUC (%)
$C_{av}$	The average drug concentration in plasma during the dosing interval (mass x volume $^{-1}$ )
$C_{last}$	Last measurable plasma concentration

$C_{max}$	The maximum (peak) observed plasma drug concentration after oral dose administration (mass x volume $^{-1}$ )
$T_{last}$	Time to reach the last measurable plasma concentration
$T_{max}$	The time to reach maximum ( $C_{max}$ ) plasma drug concentration after oral dose administration (time)
CL/F	Apparent total body clearance of drug from the plasma after oral administration (volume x time $^{-1}$ )
Vz/F	The apparent volume of distribution during terminal phase after a (single) oral administration (associated with $\lambda_z$ ) (volume)
Rsqadj 	Square of the correlation coefficient associated with $\lambda_z$
 AUC ex and Rsqadj will be used in interpretation of the primary PK parameters and therefore will be included in the listings only	

Exploratory PK analysis will be conducted using compartmental modeling when necessary. Descriptive graphical plots of individual and mean plasma concentration (per treatment) along with its time course will be generated. Further graphical exploratory analyses will be carried out if deemed appropriate. Pharmacokinetic parameters for each dose cohort will be analyzed by descriptive statistics, including the mean, SD, CV% or median (range). Since  $t_{max}$  is generally evaluated by a non-parametric method, median values and ranges will be given for this parameter. Assessment of dose-proportionality, inter- and intra-individual variability and steady-state attainment will be conducted. If appropriate, an analysis of variance (ANOVA) will be performed on log-transformed AUCs and  $C_{max}$  using a linear mixed effect model to assess day effect. Exploratory metabolite analysis on remaining plasma material from samples collected during the study will be performed, if deemed appropriate. Non-compartmental parameters, including but not limited to AUC (AUC0-tlast and/or AUC0-inf), T1/2,  $C_{max}$  and  $T_{max}$  will be reported.

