Erdafitinib exhibited a dose-related increase in Cmax and area under the analyte concentration-time curve (AUC) and time-independent PK within the dose range of 0.5 to 12 mg, both after single and multiple daily dosing. The actual sampling time to reach maximum concentration (tmax) ranged between 2-4 hours (erdafitinib as tablet), independent of the studied formulations. PK was characterized by moderate intersubject variability (CV% 31-39%) and low intra-subject variability (9-10%). Erdafitinib is primarily excreted in feces either as unchanged drug or as metabolites. In vitro data indicated that CYP3A and 2C9 are involved in erdafitinib metabolism. 70% and 20% of the radioactivity was recovered in feces and urine, respectively, with approximately 11% of unchanged drug recovered in urine. Erdafitinib is highly bound to plasma proteins, especially to  $\alpha$ 1-AGP (fraction unbound in oplasma being 0.36% and 0.50% in patients and healthy subjects, respectively. Apparent volume of distribution (Vd/F) of the terminal phase based on total plasma erdafitinib in healthy subjects is small (approximately 31 L), suggesting it is limited by the binding to plasma protein. Erdafitinib has low total plasma oral clearance (mean CL/F in subjects with cancer averaged 0.29 L/h; the corresponding value for healthy subjects was 0.43 L/h), likely restricted by protein binding. As a consequence, the apparent elimination half-life (t1/2) of erdafitinib is long (approximately 50 hours in healthy subjects) resulting an approximately 3- to 4-fold accumulation in Cmax and AUC following multiple daily dosing.

Erdafitinib is being investigated as an anti-cancer agent in several clinical studies (refer to most updated version of erdafitinib IB). As of June 2016, 305 subjects have been treated with erdafitinib. The median extent of drug exposure as of June 2016 was 7 weeks (range: 0 – 102 weeks). There does not appear to be any dose-related trends in mean or median drug exposure, suggestive of tolerability of the drug. As for clinical efficacy, responses were observed at doses of 9 mg once daily or higher (range of responses: ~12 – 40%), particularly in patients with FGFR mutations.

[figure not shown]

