#### Metabolism

To date, pharmacokinetic data have been collected in 4 clinical studies for a total of 138 cancer patients. The exposure and Cmax increased in a dose-proportional manner over the range of 25 to 225 mg once daily (QD) following palbociclib administration on days 1 and 8 of cycle 1, although some low to moderate variability around these doses was observed, particularly at the 150 mg QD dose level. Following repeated daily dosing to day 15 and day 21 (assumed to be steady state), palbociclib was absorbed with a median Tmax of ~4 h. The mean palbociclib Vz/F was 3103 L, which is significantly greater than total body water (42 L), indicating that palbociclib extensively penetrates into peripheral tissues. Palbociclib was eliminated slowly; the mean t1/2 was 26.5 h (range 15.8 to 36.2 h) and the mean CL/F was 86.1 L/h. Palbociclib accumulated following repeated dosing with a median Rac of 2.4, which is consistent with a half-life of ~27 h. Preliminary results from the recently performed food effect study (A5481021) suggested that the administration of palbociclib with food results in more consistent drug absorption and exposure than administration of palbociclib in a fasted state. As a result of these findings, patients should be instructed to take palbociclib with food. CYP3A4 inhibitors/ inducers should be avoided.

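### Non-compartmental AUC0-Inf is planned from profiles that end at 8 h, so about 90% of the erdafitinib value would be an extrapolated tail on any profile day

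*Combined protocol and SAP*

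**What the plan says.** Section 17.2.2 states: "Pharmacokinetic parameters will be determined for all patients using non-compartmental method(s"). It adds: "PK parameters listed in the table below will be estimated and reported". The table includes AUC from zero to the last measurable concentration, to 24 h and to infinity, together with Cav, Cmax, Tmax, CL/F and Vz/F. It also lists AUCex (the extrapolated percentage) and Rsqadj, which the table defines as "Square of the correlation coefficient associated with" the terminal slope. The footnote on these two says that AUCex and "Rsqadj will be used in interpretation of the primary PK parameters and therefore will be included in the listings only". Compartmental modelling is allowed if needed, as an exploratory analysis. Dose-proportionality, steady-state attainment and, if appropriate, an ANOVA for day effect on log AUCs are also planned.

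Table 10.5.1 in Section 10.6 schedules samples pre-dose and at 1, 2, 4 and 8 h on Cycle 1 Day 1 (C1D1), Cycle 1 Day 15 (C1D15) and Cycle 2 Day 1 (C2D1), and pre-dose only on Cycle 2 Day 15. Table 10.5.2 lists no later time.

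On the drugs, Section 3.3.1 says "the apparent elimination half-life (t1/2) of erdafitinib is long (approximately 50 hours in healthy subjects") and gives a tmax that "ranged between 2-4 hours (erdafitinib as tablet"). For palbociclib, Section 9.3 (Metabolism) says "palbociclib was absorbed with a median Tmax of ~4 h" and that the mean half-life "was 26.5 h (range 15.8 to 36.2 h").

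Section 2 makes erdafitinib pharmacokinetics a secondary endpoint. Palbociclib is not named there, and Section 17.2.2 calls the pharmacokinetics of the combination exploratory.

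**The concern.** A non-compartmental AUC0-Inf is the observed area plus the last concentration divided by the terminal slope. The observed part here covers 8 h of a curve that takes days to decline. With tmax at 2-4 h, only the 8 h sample, or the 4 h and 8 h samples, lie after the peak, and over that interval the concentration hardly moves. The reported number would be mostly a fitted tail resting on a slope that the data barely identify.

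The plan does not confine that number to a listing. Dose-proportionality and the ANOVA refer to AUCs without saying which. CL/F has a verbal definition with no formula. Section 10.6 lets pharmacokinetics inform a change of dosing schedule without naming a parameter. AUC0-Inf could therefore be the quantity compared across cohorts of 3-6 patients (Section 7.3).

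**Working it through.** **Reproducing the plan's own figures.** Half-life = ln 2 × (Vd/F) / (CL/F). Erdafitinib in healthy subjects (Section 3.3.1: 31 L, 0.43 L/h): 0.693 × 31 / 0.43 = 50.0 h, as stated. Accumulation at 24 h dosing = 1 / (1 − e^(−24k)) = 1 / (1 − 0.717) = 3.53, within the stated 3- to 4-fold. Palbociclib (Section 9.3: 3103 L, 86.1 L/h): 0.693 × 3103 / 86.1 = 25.0 h against a stated mean of 26.5 h. That is a ratio of means, about 6% lower, and the stated 26.5 h is used below.

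**Model (an assumption).** One compartment with first-order absorption and k = ln 2 / half-life. The absorption rate ka is solved from tmax = ln(ka/k) / (ka − k). After one dose, the area beyond time T is proportional to e^(−kT)/k − e^(−ka·T)/ka. Earlier daily doses are added by superposition: 14 before C1D15; 28 before C2D1 for erdafitinib; 21 doses and then 7 days off before C2D1 for palbociclib.

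**Share of AUC0-Inf beyond 8 h.** Erdafitinib first dose, tmax 2 h: k = 0.01386, ka = 2.638, e^(−8k) = 0.895. The share is (0.895 × 72.13) / (72.13 − 0.38) = 64.56 / 71.76 = 0.900. Palbociclib first dose, tmax 4 h: k = 0.02616, ka = 0.915, e^(−8k) = 0.811. The share is 31.01 / (38.23 − 1.09) = 0.835. In the same way:

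| Drug, half-life | C1D1 | C1D15 | C2D1 |
|---|---|---|---|
| Erdafitinib, 50 h (tmax 2-4 h) | 0.900-0.906 | 0.896-0.898 | 0.896-0.898 |
| Palbociclib, 26.5 h | 0.835 | 0.822 | 0.835 |
| Palbociclib, 15.8 h | 0.747 | 0.732 | 0.747 |
| Palbociclib, 36.2 h | 0.875 | 0.864 | 0.873 |

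A simple exponential at 15.8 h gives 0.704, hence the 70-88% range for palbociclib. If patients' erdafitinib half-life is 0.693 × 31 / 0.29 = 74 h (assumption: patient CL/F with the healthy-subject volume), the share is about 0.93.

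**Can the slope be estimated?** From 4 to 8 h after a first dose, erdafitinib falls by 5.4%, 5.2% or 4.2% for tmax of 2, 3 or 4 h. The plan does not say how many points define the slope, so both choices were tried with error-free concentrations.

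- Three points (2, 4, 8 h), first dose, tmax 4 h: the fitted log-concentration rises for both drugs at the mean half-lives, with r-squared 0.07 (erdafitinib) and 0.005 (palbociclib). No AUC0-Inf results. With erdafitinib tmax at 2 h, the fit is good (r-squared 0.998) and AUC0-Inf is 5% high.
- Three points, erdafitinib C1D15, tmax 4 h: the sign is right, but the slope is 0.0091 per hour against a true 0.0139.
- Two points (4, 8 h), first dose: AUC0-Inf is 1.00, 1.03 or 1.26 times the truth for erdafitinib (tmax 2, 3, 4 h), and 1.35, 1.30 or 1.28 times for palbociclib (15.8, 26.5, 36.2 h). On C1D15 the excess falls to 0-6% and 8-19%.

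**CL/F depends on the unstated choice.** If CL/F were dose / AUC0-Inf on C1D15, the area would include residual drug from earlier doses. Even with the slope known exactly, the ratio to true CL/F is (1 − e^(−24k)) / (1 − e^(−360k)): 0.28 for erdafitinib and 0.47 for palbociclib.

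**Does the alternative work?** First-dose AUC0-24 also has 60-66% of its area beyond 8 h, so it is no remedy on C1D1. After repeated dosing, the pre-dose concentration can stand in for the 24 h value. The linear trapezoid over 0, 1, 2, 4, 8 and 24 h, divided by dose / CL, gives:

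- Erdafitinib C1D15: 0.99 at 50 h and 0.96 at 74 h. With the visit 3 days early, as the Section 6 notes allow (11 prior doses), it gives 0.98 and 0.93.
- Erdafitinib C2D1: 1.00 at either half-life.
- Palbociclib C1D15: 1.00-1.02 over 15.8-36.2 h.
- Palbociclib C2D1: 0.34 at 26.5 h, because it follows 7 days off drug. That day must not be treated as steady state.

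**The case against.** The plan has more protection than the AUC0-Inf line suggests. It lists AUC0-24 and Cav, which are repeat-dose measures, and plans to assess steady-state attainment. AUCex would show an extrapolated share near 90%, and compartmental modelling is available. A sentence in Section 17.2.2 ties parameter calculation to the last measurable concentration, and its closing sentence allows AUC to the last measurable concentration and/or to infinity, although that sentence may concern metabolites. The sampling days are named in Section 10.6, and the word single in the Vz/F definition hints at the first dose. The two-point biases rest on a fitting choice that the plan never states.

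Much of this stands. The fix mostly specifies how to use measures already listed, and the bias figures are conditional. But AUCex can flag the tail without correcting it. No limit on AUCex or Rsqadj and no trigger for modelling is set, and AUC0-Inf remains on the list to be reported.

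Three stronger readings are not supported:

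- A reader might infer that Rsqadj would always look perfect. A squared correlation does equal 1 for any two points, but an adjusted value is undefined there, and a three-point first-dose fit with tmax at 4 h fails visibly.
- A reader might infer that CL/F, Vz/F and half-life are all lost. CL/F is affected only if taken from AUC0-Inf. In this model the errors in Vz/F largely cancel. Parent-drug half-life is affected only if the closing sentence covers it.
- A reader might infer that dose-finding is compromised. No section rests a DLT, MTD or recommended-dose decision on AUC0-Inf.

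**Conclusion.** The point holds for AUC0-Inf and for anything derived from it. Followed as written, the plan reports an erdafitinib AUC0-Inf of which about 90% is extrapolated on every full-profile day. The palbociclib share is 82-84% at the mean half-life. That second figure carries less weight because palbociclib pharmacokinetics are exploratory here.

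The shares assume one-compartment kinetics with absorption set by the stated tmax. They change little with the profile day, and for erdafitinib they rise if the half-life in patients is longer than in healthy subjects. The 0-26% (erdafitinib) and 28-35% (palbociclib) first-dose overstatements additionally assume a two-point slope and error-free data.

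Cmax, Tmax, AUC0-last and troughs remain sound. Severity is minor to moderate: a correction to the analysis of a secondary endpoint.

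**What to change.** Amend Section 17.2.2 as follows.

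1. Remove AUC0-Inf, and any parent-drug half-life, from the non-compartmental list. If they are wanted, take them from the compartmental modelling already allowed.
2. Compute AUC0-24 and Cav on C1D15 for both drugs and on C2D1 for erdafitinib only, using that day's pre-dose concentration as the 24 h value. Define CL/F as dose / AUC0-24. Use only profiles with uninterrupted, unchanged recent dosing and a recorded prior-day dose time, which Section 10.6 already asks sites to note. Fix the eligibility window in advance and report how many profiles are excluded.
3. Name this AUC0-24, Cmax and trough as the inputs to dose-proportionality. Test day effect on erdafitinib C1D15 against C2D1, or on AUC0-8 across days.
4. On C1D1, report AUC0-8, Cmax and Tmax only.

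These are wording changes with no new samples; modelling is extra work only if it is wanted. The price is that no model-free half-life is available, and C1D15 erdafitinib exposure is slightly low if the half-life is long or the visit early. Profiles after dose holds also drop out of cohorts of 3-6. Section 8.1.3.2 has phosphate peaking between Cycles 1 and 2 and rising with dose, and Section 8.4 omits erdafitinib at high phosphate levels. The retained profiles may therefore lean towards lower exposure, which is why the exclusion count should be reported.
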